7.8 Efficacy Endpoints

Efficacy will be evaluated by the LFGS, POL, pGAI, iGAI, and Swelling Assessment.

7.9 Assessment of Safety

7.9.1 Safety Endpoints

Safety of the retreatment with PN40082 will be evaluated by the nature, severity, and frequency of treatment-emergent adverse events (TEAEs). All AEs that occur during the study will be recorded whether or not they are considered to be related to treatment. A description of the AE will be recorded with the date of onset, date of resolution, severity of the AE, relationship to the study device, action taken, and the outcome.

7.9.2 Other Safety Evaluations

Adverse events of special interest, including any changes in vision and any events attributable to an embolic or ischemic cause (e.g., skin infarction), will be evaluated. Other safety evaluations are lip function, lip sensation, lip texture, lip firmness, lip symmetry, and lip movement/function.

7.9.3 Definitions of Terms

7.9.3.1 Adverse Event

An AE is defined as any untoward medical occurrence associated with the use of a drug/device in humans, whether or not considered drug/device-related (21 Code of Federal Regulations [CFR] 312.32 (a) and 803). An AE can therefore be any unfavorable and unintended sign (including an abnormal laboratory finding, for example), symptom, or disease temporally associated with the use of a drug/device, without any judgment about causality.

Expected adverse events are defined as the events that appeared at injection site subsequent to the first injection. Expected adverse events may include but are not limited to bruising, swelling, erythema, edema, and inflammation at injection site.

7.9.3.2 Suspected Adverse Reaction

A suspected adverse reaction (SAR) is defined as any AE for which there is reasonable possibility that the drug/device caused the AE (21 CFR 312.32 (a)).

7.9.3.3 Unexpected Adverse Event

An AE or SAR is considered unexpected if it is not consistent with the risk information described in the labeling for the study device.

7.9.3.4 Adverse Events of Special Interest

Certain events will require more detailed and timely reporting. These include:

- any changes in vision
- any events attributable to an embolic or ischemic cause (e.g., skin infarction)
- Any incidence of an event due to an embolic or ischemic cause or visual disturbances (including, but not limited to, any loss of vision, blurry vision, double vision, pain in or around eye, blind spot or shadow in the visual field, trouble moving eyes, etc.) MUST be immediately reported to the Medical Monitor by phone, email or fax. The investigator/coordinator must complete the AE source/CRF page and email or fax it to the Medical monitor as soon as possible after the investigator or coordinator has become aware of its occurrence. These reports will include the depth of injection, the injection volume, the symptoms that were observed, the time to onset, time to resolution, and any interventions that were implemented. The Sponsor will notify the FDA within 10 working days.

In the event of blindness or any ophthalmic signs or symptoms, subjects will undergo immediate evaluation by a retina specialist.

Refer to [Appendix 1: Filler First Aid Protocol](#).

7.9.3.5 Serious Adverse Event

An SAE is defined as any AE or SAR that, in the view of the investigator or Sponsor, results in any of the following outcomes (21 CFR 312.32 (a)):

- Death
- Life-threatening AE (Note: the term “life-threatening” as used here refers to an event that in the view of the investigator or Sponsor places the subject at immediate risk of death at the time of the event; it does not include an AE or SAE that, had it occurred in a more severe form, might have caused death [21 CFR 312.32(a)])
- Inpatient hospitalization or prolongation of existing hospitalization. See exclusion to SAE reporting below under Planned Hospitalization.
- Persistent or significant incapacity or substantial disruption of the ability to conduct normal life functions
- Congenital anomaly/birth defect
- Required intervention to prevent permanent impairment/damage

- Any “other” important medical event. Important medical events that may not result in death, be life-threatening, or require hospitalization may be considered serious when, based upon appropriate medical judgment, they may jeopardize the subject and may require medical or surgical intervention to prevent one of the outcomes listed in this definition. Examples of such medical events include allergic bronchospasm requiring intensive treatment in an emergency room or at home, blood dyscrasias or convulsions that do not result in inpatient hospitalization, or the development of drug dependency or drug abuse.

7.9.3.6 Planned Hospitalization

A hospitalization planned by the subject prior to signing the ICF is considered a therapeutic intervention and not the result of a new SAE and should be recorded as medical history. If the planned hospitalization or procedure occurs as planned, the record in the subject’s medical history is considered complete. However, if the event/condition worsens during the study, it must be reported as an AE.

7.9.4 Pregnancy

Pregnancies occurring after administration of study device require immediate reporting. They must be reported within 24 hours after the investigator has become aware of the pregnancy. A pregnancy report will be completed and sent by fax to the Sponsor or designee within 24 hours of becoming aware of the pregnancy. The investigator will collect follow-up information regarding the outcome of the pregnancy and any postnatal sequelae in the infant that must also be reported to the Sponsor or designee. Upon awareness of the outcome of the pregnancy, the Principal Investigator or designee must forward a follow-up Pregnancy Report with any relevant information to the Sponsor or designee.

If the outcome of the pregnancy meets the criteria for immediate classification of an SAE (e.g., spontaneous abortion, stillbirth, neonatal death, or congenital anomaly), the investigator will report the event by faxing a completed SAE report form to the Sponsor or designee within 24 hours of being notified of the pregnancy report.

The subject should immediately be withdrawn from the study.

7.9.5 Monitoring Adverse Events

Each subject will be monitored for the occurrence of AEs, including SAEs, immediately after treatment initiation. Each subject will be followed for safety monitoring until discharged from the study. Follow-up procedures related to pregnancy or AEs or SAEs may continue beyond the end of the study.

Subjects will be questioned and/or examined by the investigator or a qualified designee for occurrence of AEs throughout the study. The presence or absence of specific AEs should not be elicited from subjects. In addition, subjects will be instructed to record AEs on the subject diary card during the 2 weeks after treatment. Subjects having AEs will be monitored with relevant clinical assessments and laboratory tests, as determined by the investigator.

AEs, actions taken as a result of AEs, and follow-up results must be recorded on the CRF, as well as in the subject’s source documentation.

For all AEs that require the subject to be withdrawn from the study and SAEs, relevant clinical assessments will be repeated as clinically appropriate until final resolution or stabilization of the event(s).

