7 INVESTIGATIONAL PLAN

7.1 Overall Study Design

This is a multicenter, open-label clinical study of retreatment of subjects seeking lip augmentation who received treatment with either PN40082 or Restylane Silk in prior Protocol PRO 2018-02. Subjects meeting the inclusion/exclusion criteria will receive a single additional treatment with PN40082.

Visits and telephone contacts will occur at:

Visit 1 / Day 1 – baseline and treatment. This is the same visit as Visit 5 (Day 168) of Protocol PRO 2018-02.

-Day 3 (± 2 days) - Safety follow-up telephone call

-Day 14 (± 2 days) – Safety follow-up telephone call

Visit 2 / Day 28 (± 2 days) / Month 1 – Interim Visit

Visit 3 / Day 56 (± 4 days) / Month 2 – End of Study (EOS) Visit

-Day 168 (± 7 days) – Safety follow-up telephone call

Efficacy evaluations are:

Lip Fullness Grading Scale (LFGS) - overall lip fullness considering both lips together, fullness of the upper lip, and fullness of the lower lip

Perioral lines at rest severity scale (POL) - overall perioral lines at rest severity considering both lips together, perioral lines at rest severity of the upper lip, and perioral lines at rest severity of the lower lip

Patient Global Aesthetic Improvement (pGAI)

Investigator Global Aesthetic Improvement (iGAI)

Safety will be assessed by monitoring adverse events (AEs) at all study visits. Adverse events of special interest, including any changes in vision and any events attributable to an embolic or ischemic cause (e.g., skin infarction), will be monitored. Other safety evaluations are lip function, lip sensation, lip texture, lip firmness, lip symmetry, and lip movement/function.

Other evaluations are Investigator Ease of Use Assessment, Swelling Assessment, and Subject Satisfaction with Lips Assessment.

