7.6.5 Vision Evaluations

Subjects will be assessed with Snellen visual acuity, confrontational visual fields, and ocular motility by a trained evaluator. These assessments will be performed at Visit 1/Day 1 prior to treatment and repeated 30 minutes following treatment and at Visit 2/Month 1 and Visit 3/Month 2.

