8.3 Safety Analysis

Adverse events will be coded to system organ class and preferred terms using the Medical Dictionary for Regulatory Activities (MedDRA, Version 20 or higher).

Frequency and percentage of subjects reporting TEAEs will be tabulated overall and for each treatment in PRO 2018-02 by preferred terms and further by severity and relationship to study device. In summaries of severity and relationship, subjects reporting more than one event in a treatment arm that are mapped to the same preferred term will be counted only once in that treatment arm under the strongest severity and relationship, respectively. In addition, visual related TEAEs will be summarized separately by preferred term.

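### The rule against eliciting specific AEs has no visible exception for events of special interest, so between examinations transient visual symptoms and skin ischemia depend on open questioning, a 2-week diary and unscheduled contact

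*Protocol*

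**What the plan says.** Protocol Section 7.9.5 sets the general method: "Subjects will be questioned and/or examined by the investigator or a qualified designee for occurrence of AEs throughout the study". It then limits that method: "The presence or absence of specific AEs should not be elicited from subjects". Nothing in the visible text restricts the second sentence to ordinary AEs.

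Other sections single out a small group of events. Section 7.1 says that changes in vision and "any events attributable to an embolic or ischemic cause (e.g., skin infarction), will be monitored". Section 7.9.2 repeats the commitment: "any events attributable to an embolic or ischemic cause (e.g., skin infarction), will be evaluated". Section 7.9.3.4 opens with "Certain events will require more detailed and timely reporting", gives a list of visual symptoms, and requires immediate notification of the Medical Monitor. Section 8.3 adds that "visual related TEAEs will be summarized separately by preferred term".

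Vision is also examined directly. Section 7.6.5 calls for acuity, visual fields and ocular motility testing by a trained evaluator, "prior to treatment and repeated 30 minutes following treatment and at Visit 2/Month 1 and Visit 3/Month 2". The Day 3, Day 14 and Day 168 calls (Sections 7.7.2 and 7.7.5) list three tasks only: AEs, concomitant medications or treatments, and adherence to the prohibitions.

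**The concern.** The protocol promises to watch for a named set of events, several of them defined by symptoms that only the subject can report. It also tells staff, without a visible exception, not to ask about specific events. The reporting duty in Section 7.9.3.4 begins when the site becomes aware of an event; it is not an instruction to ask. A caller following Section 7.9.5 would put an open AE question and stop there.

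The interpretation of a low or zero count is at stake. The SAP gives vascular/visual TEAEs nine table shells (14.3.2.1 to 14.3.2.9), so these counts will be prominent in the report. Where an event was looked for, its absence is informative. Where it could be found only if the subject thought to mention it, absence is less informative. The report needs to let the reader tell these apart.

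**Working it through.** The plan states no event rate, power or detection figure for these events, so there is nothing of its own to reproduce. The check sets out who can find what, and when.

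**Step 1. Planned routes of detection, at nominal days** (Protocol Section 2, Sections 7.4.2, 7.6.5, 7.6.22 and 7.7)

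| Period | Vision test | Other planned routes |
|---|---|---|
| Day 1 | Before treatment and 30 minutes after | Injector's observation of blanching |
| Between Day 1 and Day 28 | None | Calls on Day 3 and Day 14; open diary for 2 weeks |
| Day 28 | Yes | AE assessment; lip assessments |
| Between Day 28 and Day 56 | None | None |
| Day 56 | Yes | AE assessment; lip assessments |
| Day 57 to Day 168 | None | One call |

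Unscheduled visits are possible throughout, with vision testing if needed (Section 7.7.6). No row of the schedule is a skin-color or perfusion assessment. An investigator examining the lips may see an ischemic lesion, but those assessments cover function, sensation, texture, firmness, symmetry and movement.

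**Step 2. Length of the final gap**

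- Day 57 to Day 168 inclusive: 168 − 57 + 1 = 112 days.
- Share of the 167 days after treatment (168 − 1): 112 / 167 = 67%.
- Shortest interval from Visit 3 to the call, using the windows: (168 − 7) − (56 + 4) = 101 days.
- Longest: (168 + 7) − (56 − 4) = 123 days.

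**Step 3. What incomplete capture would do to a zero count (illustration only)**

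Let s be the probability that a true event is captured by any route. The documents give no value for s, so those below are assumptions. With zero events in N subjects, the one-sided 95% upper limit for the captured rate is 1 − 0.05^(1/N). Dividing by s gives the limit for the true rate. N = 158 is the PRO 2018-02 enrollment, which the synopsis expects this study to fall below. N = 80 is assumed.

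| N | s = 1 | s = 0.7 | s = 0.5 |
|---|---|---|---|
| 158 | 1.88% | 2.68% | 3.76% |
| 80 | 3.68% | 5.25% | 7.35% |

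The chance of capturing at least one event at an assumed true rate of 1% with N = 158 is 1 − (1 − 0.01s)^158. This gives 0.80, 0.67 and 0.55 for s = 1, 0.7 and 0.5. These limits are mine; SAP Section 5.1 plans no inferential analysis. They show how sensitive the reading of a zero is to s and say nothing about the actual value of s.

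**The case against.** The strongest reply is that much of the ascertainment is active. Vision is tested at four scheduled time points whether or not the subject complains. SAP Listing 16.2.4.7 records whether vision changed significantly from the PRO 2018-02 baseline, and Table 14.3.2.1 separates reports by subject from reports by the PI. Open questioning at every visit and call is itself active. The diary covers the first 2 weeks, the injector watches for blanching, and Appendix 1 has emergency contacts given to subjects. A reader might infer that the visual and ischemic counts rest entirely on what subjects volunteer. For vision these provisions rule that out, and for ischemia investigator observation is a further route.

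Three further points have weight. Section 7.9.5 says should not, so it is not an absolute ban on asking. The suspension triggers in Section 7.9.9 are embolic events that lead to skin necrosis, vision loss or stroke; a subject asked an open question is unlikely to leave those out. Appendix 1 describes visual signs as usually immediate, so the long late gap matters less for embolic vision events than its length suggests. Avoiding prompts is also a recognized choice, applied to swelling in Section 7.6.14.

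What remains is narrower. A visual symptom that resolves between tests may leave nothing to measure, skin ischemia has no scheduled assessment of its own, and the calls contain no question on either. The By Subject and By PI split does not distinguish elicited from volunteered events, or examination findings from other PI reports.

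**Conclusion.** The point holds in a limited form. Section 7.9.5 and the monitoring commitments in Sections 7.1 and 7.9.2 are not reconciled for the 7.9.3.4 events. The effect falls on transient visual symptoms and skin ischemia arising between examinations, including a nominal 112 days after Month 2 (101 to 123 with windows) covered by one call.

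The size of any under-capture cannot be known from the documents. A reader might infer that a large fraction of these events would be lost, for instance that reported rates would be half the true ones. Nothing in the documents supports such a figure, and it would ignore the scheduled vision tests. No planned test or decision limit is affected, because the study is descriptive.

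The conclusion assumes that no exception exists elsewhere. Part of Section 7.9.7, the CRFs and any call scripts were not available to check. If one of them already permits targeted questions, Section 7.9.5 needs only a cross-reference.

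**What to change.** - **Section 7.9.5:** except the events of Section 7.9.3.4 from the non-elicitation rule.
- **Sections 7.7.2 and 7.7.5:** after the open AE question, add one scripted question on the visual symptoms listed in Section 7.9.3.4 and one on skin color change or skin breakdown. Asking them second keeps the volunteered count intact.
- **CRF:** add a flag for events that came to light through a scripted question.
- **SAP Tables 14.3.2.1 to 14.3.2.9 and Listing 16.2.7.1.1:** show volunteered, elicited and examination-detected events separately. Several of these shells label their overall row as injection-site or visual TEAEs, so the 7.9.3.4 events should be identifiable within that group.
- **If the calls have already been made:** the study report should describe how these events were ascertained and separate examination findings from spontaneous reports as far as the data allow.

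The cost is two questions per call, one CRF field and a further split in the shells. The drawback is that elicited events may not be comparable with PRO 2018-02 counts, whose method of elicitation is not described here. The flag allows them to be set aside for that comparison.

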7.9.6 Assessment of Adverse Events

7.9.6.1 Assessment of Severity

Severity of AEs will be graded according to the following definitions:

Mild: AE that was easily tolerated

Moderate: AE sufficiently discomforting to interfere with daily activity

Severe: AE that prevented normal daily activities

7.9.6.2 Assessment of Causality

A medically qualified investigator must assess the relationship of any AE (including SAEs) to the use of the study device as unlikely related, possibly related, or probably related based on available information, using the following guidelines:

Unlikely related: no temporal association, or the cause of the event has been identified, or the study device cannot be implicated based on available information

Possibly related: temporal association but other etiologies are likely to be the cause; however, involvement of the study device cannot be excluded based on available information

Probably related: temporal association, other etiologies are possible, but unlikely based on available information

7.9.6.3 Reference Safety Information for Assessing Expectedness of Adverse Events

For reference safety information for assessing the expectedness of an AE for the study device in this study, see [Appendix 2: PN40082 Instructions for Use](#).

The investigator must provide a follow-up written report within 5 calendar days of reporting the event to the medical monitor. The written report must contain a full description of the event and any sequelae. Subjects who have had an SAE must be followed clinically until all parameters (including laboratory) have either returned to normal or are stabilized.

7.9.8 Diary Assessments

Diaries will be reviewed by the study staff each time they are returned by a subject. Entries will be reviewed for completeness and medical accuracy. Any diary events listed by the subject as persisting beyond the final recording day of the diary will be evaluated by the Investigator and may be recorded as an AE at the discretion of the Investigator.

7.9.9 Criteria for Early Termination of the Study

The trial may be terminated because of safety concerns. If termination is deemed appropriate, there will be timely communication with the FDA in accordance with the regulations (21 CFR 812.150 (devices)). The sponsor, Prolenium Medical Technologies, will initiate discussion as soon as possible about the appropriate course of action for the trial in question and for the investigational product. There will be immediate follow-up by the company to investigate any potential safety concern.

In the event of a vascular embolic event leading to skin necrosis, vision loss, or stroke, enrollment and treatment at the investigational site will be suspended and a root cause investigation will be conducted to determine the cause of the embolic event and whether the outcome was anticipated (the investigator did not properly follow the treatment SOP) or unanticipated (the investigator did properly follow the treatment SOP). If the latter situation is observed, the entire study will be immediately suspended and no subjects will be enrolled until the event can be properly characterized and an appropriate treatment strategy to avoid this unanticipated event can be devised.

7.9.10 Withdrawal Due to Safety Observations

See Section 7.3.3 for the criteria for withdrawing a subject. If a subject is withdrawn from the study, the activities specified for Visit 3/Month 2 on the schedule of study activities (Section 2) should be completed if possible.

8 STATISTICAL METHODS

Prior to the database lock, a detailed, finalized Statistical Analysis Plan will be completed and placed on file. The Statistical Analysis Plan will contain a more comprehensive explanation than that provided here of the methodology used in the statistical analyses, as well as the rules and data handling conventions used to perform the analyses and the procedure used to account for missing data. Data will be summarized overall and also broken down by the treatment arm in PRO 2018-02.

8.1 Analysis Populations

Safety and efficacy results will be summarized descriptively for all subjects who receive retreatment in this study.

8.2 Efficacy Analysis

Change from baseline in this study and change from baseline in the prior controlled study will be summarized for LFGS and POL. Other efficacy variables include pGAI, iGAI, and Swelling Assessment at Visit 3/Month 2.

8.3 Safety Analysis

Adverse events will be coded to system organ class and preferred terms using the Medical Dictionary for Regulatory Activities (MedDRA, Version 20 or higher).

Frequency and percentage of subjects reporting TEAEs will be tabulated overall and for each treatment in PRO 2018-02 by preferred terms and further by severity and relationship to study device. In summaries of severity and relationship, subjects reporting more than one event in a treatment arm that are mapped to the same preferred term will be counted only once in that treatment arm under the strongest severity and relationship, respectively. In addition, visual related TEAEs will be summarized separately by preferred term.

